A multicenter comparative diagnostic accuracy study

 Diagnostic tools to establish the presence and severity of peripheral arterial disease in people with diabetes (**DM PAD**)

Statistical Analysis Plan
CONFIDENTIAL

Version No	V1.0
Date Finalised	14 November 2023
Author(s)	[name] (until unblinded on 01 Feb 2023), [name] (from Feb 2023)
CI Name	[name], St Marys Hospital
CI Email address	[contact] ; [contact]

Signatures	
Trial Statistician: [name] 	Date: 2023-11-14
Chief Investigator: [name] 	Date: 2023-11-14
Designee Chief Investigator: [name] 	Date: 2023-11-14

Document Control		
Version No	Date	Summary of Revisions
1.0	14Nov2023	Initial Creation

Table of Contents

List of Abbreviations	3
1. Introduction	4
2. Statistical Methods section from the protocol	4
3. Overall Statistical Principles	6
3.1 SAP objectives	6
3.2 Analysis population	6
3.3 General	6
3.4 Determining PAD diagnosis from Index test results	7
3.5 Determining PAD diagnosis from Reference test results	7
4. Final Analysis	8
4.1 Recruitment and retention	8
4.2 Baseline data	8
4.3 Graphical analysis	9
4.4 Primary outcome	9
4.5 Secondary analyses	9
4.5.1 ROC analysis	9
4.5.2 Combinations of tests	10
4.6 Sensitivity analysis	11
4.7 Subgroup analyses	11
5. Validation and QC	11
6. Data sharing	11
7. References	12

List of Abbreviations

Abbreviation	Full name
ABPI	Ankle brachial pressure index
AE	Adverse Event
BMI	Body Mass Index
CI	Chief Investigator
CTA	Computed tomography angiography
DFU	Diabetic foot ulcer
DP	Dorsal Pedis
ECTU	Edinburgh Clinical Trials Unit
egFR	Estimated glomerular filtration rate
EQ-5D-5L	European Quality of Life-5 dimensions 5 Level
IQR	Inter-quartile range
MRA	Magnetic resonance angiograph
PAD-scan	Podiatry ankle duplex scan
PT	Posterior Tibial
QALY	Quality Adjusted Life Years
ROC	Receiver Operating Characteristics
SAE	Serious Adverse Event
SAP	Statistical Analysis Plan
SOP	Standard Operating Procedure
TBPI	Toe-brachial pressure index
TcPO2	Transcutaneous pressure of oxygen
TrEAD	TEsting for Arterial disease in Diabetes study
WIFI	Wound, ischaemia, and foot infection

1. Introduction

This is a prospective multicentre diagnostic accuracy study comparing the diagnostic performance, powered to compare five index tests (the sixth exploratory test in four sites) in the diagnosis of peripheral arterial disease (PAD) in patients with diabetes against a reference test (CTA or MRA). The tests shall be performed in the following order:

1. Audible handheld Doppler
- 2a. Visual handheld Doppler
- 2b. PAD-scan (in 4 selected centres)¹
3. Toe-brachial pressure index (TBPI)
4. Ankle-brachial pressure index (ABPI)
5. Exercise ABPI i.e. ABPI performed following repetitive heel raising.

Participants will firstly be assessed via remote screening. If considered eligible, they will be invited in for a face-to-face appointment (i.e. Visit 1) alongside a routine/planned visit. They will then be invited for a reference scan (i.e. Visit 2) within 6 weeks of Visit 1. Finally a subset of patients will be invited to a 1 year follow up. The target sample size is 584 participants from 18 sites.

This document has been compiled according to the Edinburgh Clinical Trials Unit (ECTU) standard operating procedure (SOP) "Statistical Analysis Plans" ECTU_ST_04 and has been written based on information contained in the study protocol version 5.0 25 July 2022.

2. Statistical Methods section from the protocol

The five individual tests (and the sixth exploratory test in four sites) will be compared against the reference test (CTA/MRA), calculating standard diagnostic accuracy metrics of sensitivity, specificity, predictive values, likelihood ratio, and diagnostic odds ratio (using the bivariate model approach implemented in R).

95% confidence intervals calculated at 99% to adjust for the five comparisons will be presented.

The robustness of the findings to any observed patterns of missing data will be assessed, which are expected to differ by test. A multiple imputation approach will be used assuming the data are missing at random. In addition, and probably more consistent with the likely missing data generating mechanisms, sensitivity type analyses assuming the data are missing not at random (i.e. informatively missing) will be explored. This would attempt to identify different types of missing data by an underlying reason or reasons, and then imputing values that capture plausible measurements for those missing data. The (gamma) γ -adjustment approach given by van Buuren will be followed (Flexible Imputation of Missing Data, Chapman and Hall, 2018, section 3.8ff), and also the recommendations of Molenburghs & Kenward (Missing Data in Clinical Studies, Wiley, 2007; Section 19ff on sensitivity analyses). These approaches would allow the set of reasons for missing values to vary across the tests. The purpose is to stress the calculated findings to test their robustness to the observed patterns of missing data.

¹ In four selected centres, participants will be 1:1 randomised either to receive the visual handheld Doppler assessment first or the PAD-scan first. These participants will receive six tests in total (excluding reference tests) as oppose to five.

Statistical Analysis Plan	DM PAD
Version No	V1.0
Date Finalised	14 November 2023

The subgroups of disease severity (both clinically and radiologically defined as detailed below) will be explored and those with/without neuropathy or DFU. Any further subgroup analysis (e.g. if suggested later by new data external to the study) will be labelled exploratory. Pre-specified subgroup analyses will be unlikely to be adequately powered. Clinical severity will be graded according to the severity of symptoms (from least to most severe; asymptomatic, intermittent claudication, rest pain and tissue loss). Severity will be measured radiologically using the ANGIO-score as outlined in section 5.7. Both will be analysed as pre-specified subgroup analyses in the Statistical Analysis Plan.

Combinations of tests will be explored to see if using more than one test has incremental diagnostic value. The combinations of tests that were clinically felt to potentially offer an improvement over individual tests and acknowledging the paired data, use the approach of Pepe and Thomson (Biostatistics, 2000; 1, 2; 123-140 'Combining diagnostic test results to increase accuracy'), which looks at linear combinations of the underlying tests. Post-hoc checks will be made if there were combinations that were not pre-specified that performed even better, as hypotheses for subsequent evaluation.

It is important to quantify the ability of each of the 5 index tests to measure consistently the same measurement of interest on the same leg of the same subject using the same test kit in the same location and the same environmental conditions, within a short period of time. This quantification of the intra-rater repeatability (or reproducibility) will be undertaken using the test-retest approach (35,36). The inter-rater reliability (the agreement between two or more clinicians measuring the same subject, again as under the conditions above) using appropriate methodology (35,36) will be quantified. For the inter- and intra-rater repeatability, we will aim for a sample size of 100 per pair of index tests.

These reliability studies will be performed at the start of the study and analysed as soon as the data are mature. If an index test has unacceptable intra-rater repeatability, or unacceptable inter-rater reliability, it could be dropped from further consideration, following discussions with the independent TSC. Unacceptable intra- and inter-rater reliability will be assessed in two ways—first, in an absolute sense, by looking at the kappa statistics and using the published guidance as to what an acceptable magnitude is (Fleiss, J.L. (1981). Statistical methods for rates and proportions (2nd ed.). New York: John Wiley) with a kappa of <0.4 considered unacceptable. This is not unanimity over interpreting the magnitude of kappa statistics, so our second approach will compare the kappa statistics across the tests, and label unacceptable any tests that are substantially worse than the other tests.

Inter- and intra-rater reliability will also be assessed for the reporting of reference tests using the methods outlined above. Reference tests will not be repeated due to feasibility and ethical considerations.

Index test diagnostic thresholds

The performance of the index tests based on prespecified diagnostic thresholds for PAD will be evaluated. These thresholds have been selected as they demonstrated optimal diagnostic performance in the TrEAD study or are commonly used in clinical practice. However, other thresholds have been described in the literature and there is no consensus as to which are best. Therefore, different 'exploratory' thresholds will be evaluated as part of our secondary analyses. Tests generating continuous results (ABPI, TBPI and exercise ABPI) will be evaluated for performance based on optimised thresholds derived from Receiver Operating Characteristics (ROC) analysis. A 'net benefit' approach will be used (as a sensitivity type analysis over a range of plausible thresholds) following ideas for assessing the clinical utility of prognostic models summarised in Riley R et al

(Prognostic Research in Health Care; 2018; Oxford; section 7.4.3 page 168-170). From this, it should be possible to integrate cost-effectiveness parameters into assessing the best threshold.

Diagnostic thresholds:

- o Visual waveform assessment- monophasic or biphasic waveforms with adverse features.*
- o Audible waveform assessment- monophasic waveform*
- o ABPI- ≤ 0.9 in either vessel*
- o TBPI- < 0.75 in either vessel*
- o Exercise ABPI (31)- Post exercise ABPI ≤ 0.9 in either vessel.*

3. Overall Statistical Principles

3.1 SAP objectives

The objective of this SAP is to describe the statistical analyses contributing to the final report and publication(s) of the DM PAD study. All analyses detailed in the study protocol are addressed with the exception of the internal pilot of the study which will be documented separately.

3.2 Analysis population

The analysis datasets are detailed below. All analyses will be performed on the intention to treat (ITT) population unless otherwise specified.

The trial population will include all participants who have been recruited into this trial, and who did not withdraw consent for any of their data to be stored in the trial database.

3.3 General

In general terms, categorical data will be presented using counts and percentages, whilst continuous variables will be presented using the mean, median, standard deviation (SD), minimum, maximum, Q1, Q3, inter-quartile range (IQR) and number of patients with an observation (n).

The comparison group here is diagnostic technique, so where applicable results will be split by diagnostic tests.

A further reporting metric is the number of participants who were included in the analysis, which will be supported for each of the primary (section 4.4) and secondary (section 4.5) analyses by the preparation of a STARD-style flow chart showing the 'pipeline leakage' from participants who were enrolled, to participants included in the analysis.

Where there is missing data for an outcome variable, in the first instance, those individual cases will be removed from any statistical analysis relating to that outcome variable (i.e. complete case analysis), unless otherwise specified. In tabulations, numbers of missing observations will be provided, but percentages will not include them.

All analysis and data manipulation will be carried out using SAS [1] unless otherwise stated.

Qualitative or health economic analysis will not be covered by this SAP. However, data from the statistics report may be used for health economics analyses.

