5.6 Data collection

A screening log will identify all approached patients and reasons for non-participation.

- Demographics: age, gender, equality and diversity information, diabetes type, history of smoking, retinopathy, chronic kidney disease, ischaemic heart disease, stroke and heart failure
- Foot history: PAD symptoms, previous history of DFU or amputation
- Foot examination: neuropathy, presence of DFU, DFU severity using the WIfI classification system (27)
- Quality of Life questionnaire: the validated EuroQoL (EQ-5D-5L) questionnaire will be used to assess the generic QoL at visit 1.
- Technical success of index tests: inability to perform, refusal and discontinuation of tests will be documented
- Results of index tests
- Evaluation of patient acceptability: patients will be asked to rate their experience of each test on a Likert scale (**Appendix**)

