Exercise ABPI traditionally requires a treadmill. This limits its use in primary care, where a treadmill is not available. Additionally, the results of the patient and public involvement (PPI) work suggest that 43% of patients will not be able to walk on a treadmill (due to disability, frailty or DFU) and that an additional visit to a vascular laboratory for this test would not be acceptable. To ensure patient acceptability, repetitive heel raising will be used. This can be performed in clinics, has excellent correlation with treadmill testing (28,29) and has been advocated by the American Heart Association (30). Our PPI focus group considered this test acceptable.

The exercise ABPI protocol, will consist of 50 consecutive repetitions of active dorsiflexion whilst standing (28). The knees should be kept fully extended. Participant will be allowed fingertip support against a wall to assist with balance. The protocol will be symptoms limited, so that premature termination of exercise will be permitted if the subject experiences lower limb discomfort, chest pain, shortness of breath or feels unwell for any other unspecified reason. Instances of premature termination, and accompanying reasons, will be recorded. ABPI will be measured using the same methodology as outlined above.

In some patients, exercise ABPI may not be possible due to deformities of the foot, e.g., those with forefoot amputation, Charcot foot syndrome and forefoot plantar ulceration. Foregoing exercise ABPI will be left to the clinical teams discretion. Reasons for foregoing exercise ABPI will be documented.

- **TBPI**

Measurements will be made using the Huntleigh toe pressure kit (Huntleigh Healthcare Ltd., Cardiff) employing an infrared sensor placed on the hallux.

Brachial artery pressures from both arms will be taken and the highest reading used to calculate the TBPI.

- **Audible handheld Doppler**

Audible CW Doppler interrogation of the dorsalis pedis and posterior tibial artery (Dopplex D900 Audio only Doppler, Huntleigh Healthcare Ltd., Cardiff).

- **Visual handheld Doppler**

Visual CW interrogation of the dorsalis pedis and posterior tibial artery using the handheld Huntleigh Digital Dopplex device (Huntleigh Healthcare Ltd., Cardiff). The pseudonymised visual blood flow waveforms will be saved and may be used for future analysis.

- **PAD-scan (in selected centres)**

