8. STATISTICAL ANALYSES

8.1 Sample Size and power considerations

Summary of sample size calculations

Assuming PAD prevalence of 50%, with 255 with PAD and 255 without PAD, the study will have 90% power to estimate an assumed sensitivity (or specificity) to a precision of the half width of the 95% confidence interval of 8.2%. For a sensitivity (or specificity) of 80% this half width would increase to 10.2%. The level of significance was set at 1% to adjust for the 5 tests and ensure the overall level of significance does not exceed 5%. Power calculations used R.4.0.0 power.diagnostic.test in package MKmisc. The sample sizes for estimating likelihood ratios will also be estimated.

In the TrEAD study, PAD prevalence was 66%. As there will also be recruitment from primary care, with a lower PAD prevalence (34), the estimate to reflect the findings of our systematic review have been adjusted; prevalence of 50% across 18 studies (11). In TrEAD, TBPI could not be performed in 20% of patients. A similar proportion may be unable to tolerate exercise ABPI. It is estimated that 10% of patients may drop out prior to the reference test. Therefore, the sample size has been inflated by the cumulative missingness across all groups (30%) to be certain of having enough power for each and every test comparison. Thus, we aim to recruit a total of 730 patients.

During a study monitoring meeting in February 2023 with the funder, NIHR, it was agreed for the study sample size to be reduced from 730 to 584 based on the current attrition rate of 13% (as opposed to 30% estimated when the trial was designed). To account for those participants that may not get their reference test performed within the set time frame, a final recruitment target of 600 was agreed with the NIHR in August 2023.

Details of sample size calculations

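### The SAP gives patient acceptability no analysis of its own, and its default denominator may leave out patients who refused or never started a test

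*SAP*

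**What the plan says.** Protocol 2.2 lists patient acceptability as a secondary objective and 2.4 lists it as a secondary endpoint. Protocol 5.6 defines the measurement: "patients will be asked to rate their experience of each test on a Likert scale". It refers to an appendix for the form, which is not in the text available.

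The same section records non-performance under a separate heading: "Technical success of index tests: inability to perform, refusal and discontinuation of tests will be documented". Technical success is a secondary endpoint in its own right (Protocol 2.4). Protocol 5.7 adds that reasons for not doing exercise ABPI, and for ending the exercise early, are recorded.

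Protocol 8.1 expects non-performance to be substantial for two tests. For TBPI: "In TrEAD, TBPI could not be performed in 20% of patients". For exercise ABPI: "A similar proportion may be unable to tolerate exercise ABPI".

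SAP 3.1 states that every protocol analysis except the internal pilot is covered. Sections 4.1 to 4.7 nevertheless contain no analysis of acceptability or of technical success. What remains is SAP 3.3. For a missing outcome, "those individual cases will be removed from any statistical analysis relating to that outcome variable (i.e. complete case analysis), unless otherwise specified". For tables, "In tabulations, numbers of missing observations will be provided, but percentages will not include them".

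**The concern.** Refusing a test, or being unable to tolerate it, is direct evidence about its acceptability. If such patients leave no rating, the default removes them from the denominator, and the percentage describes patients who accepted the test rather than patients to whom it was offered.

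The effect would differ by test: small where nearly everyone can be tested, larger for exercise ABPI and TBPI. A reader comparing acceptability across tests could then be misled. The matter is relevant to exercise ABPI in particular, because Protocol 5.7 chose heel raising over a treadmill on grounds of patient acceptability.

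Nothing elsewhere in the SAP guards against this. The imputation in SAP 4.6 is optional and confined to the primary outcome. The flow charts promised in SAP 3.3 cover only the analyses in 4.4 and 4.5, which do not include acceptability.

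**Working it through.** The documents give no acceptability figure, so there is nothing to reproduce. The calculation shows how far the default percentage could differ from one based on everyone offered the test.

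**Inputs**
- Participants: N = 600, the recruitment target (Protocol 8.1). N cancels and only makes the counts concrete.
- Unrated share: m = 20%, from Protocol 8.1 for TBPI and exercise ABPI. That gives 120 unrated and 480 raters. Treating all non-performance as unrated is an assumption.
- Share of raters who find the test acceptable: a = 70%, 80% or 90% (assumption).
- Share of the unrated who refused or could not tolerate the test: s (unknown; varied). The rest are set aside as not applicable.

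**Formulas**
- SAP default: 480a / 480 = a.
- Among those offered the test: 480a / (480 + 120s).
- Overstatement: the difference, which equals a × s / (4 + s).

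**Results**

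| s | a = 70% | a = 80% | a = 90% | Overstatement (points) |
|---|---|---|---|---|
| 100% | 336/600 = 56.0% | 384/600 = 64.0% | 432/600 = 72.0% | 14.0 to 18.0 |
| 50% | 336/540 = 62.2% | 384/540 = 71.1% | 432/540 = 80.0% | 7.8 to 10.0 |
| 25% | 336/510 = 65.9% | 384/510 = 75.3% | 432/510 = 84.7% | 4.1 to 5.3 |
| 0% | 70.0% | 80.0% | 90.0% | 0 |

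**If unrated patients are not all unfavourable.** Let q be the share of the 120 who would have found the test acceptable. Among all 600 the percentage is (480a + 120q) / 600. With a = 90% and q = 50%, this is (432 + 60) / 600 = 82.0%, a gap of 8 points. With q = a it is 90.0%, and the gap is zero.

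**If fewer are unrated.** With s = 100%, the gap is m × a. At m = 10% it is 7 to 9 points, and at m = 5% it is 3.5 to 4.5 points.

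**Effect on a comparison.** Suppose one test is done in everyone and 80% find it acceptable, while another is unrated in 20% and acceptable to 90% of raters. The default shows a 10-point advantage for the second. If half of its unrated patients refused or could not tolerate it, both stand at 80.0%.

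**The case against.** Four objections have force.

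- **The rating rule is not stated.** A reader might infer that only patients who underwent a test rate it. Protocol 5.6 says only that patients rate their experience of each test, and the form cannot be checked for a refused or not-done option. Exercise ABPI is symptom-limited (Protocol 5.7), so a patient who stops early has had the test and may rate it poorly. The exposure is therefore mainly refusals and tests never started.
- **Non-performance is not the same as dislike.** A reader might infer that the bias is always upward. But Protocol 5.7 says "In some patients, exercise ABPI may not be possible due to deformities of the foot", and leaves the decision not to do the test to the clinical team. The 20% for exercise ABPI is a planning guess carried over from TBPI, and the TBPI figure is for tests that could not be performed, not a refusal rate. Protocol 8.1 also reports attrition of 13% against the planned 30%. If that covers the same components, which is not stated, non-performance may be below 20%.
- **Refusals are not lost.** They are documented under technical success, and missing counts must be shown. Ratings among users beside a separate failure rate is a legitimate way to report. However, technical success has no analysis in the SAP either, and a bare missing count does not separate refusal from impossibility or a blank form.
- **There is no planned tabulation to be wrong.** SAP 3.3 is a general default, and no cut of the scale or comparison between tests is specified. This is correct, and it is why the point rests on the missing analysis. Without a specific rule, the default is what would be applied.

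**Conclusion.** The point holds in a limited form. Acceptability has no analysis in the SAP, and under the default denominator it may be reported only for patients who accepted each test. With 20% unrated and an assumed 70 to 90% acceptable among raters, the overstatement ranges from zero to 18 points, depending mainly on how much non-performance is refusal or intolerance. The documents do not give that split.

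They do not support saying that acceptability will be overstated, or that exercise ABPI alone is favoured. TBPI carries the same 20%, and if the reasons were similar the two would not be misranked against each other. The primary endpoint is unaffected. A short addition to the SAP is justified because the endpoint is otherwise undefined and the information needed is already being documented.

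**What to change.** Add a paragraph to SAP 4.5 that reports acceptability for each test in two ways:

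- **(a) Among raters**, with the number of raters stated.
- **(b) As a sensitivity summary, among all participants offered the test.** Count refusals, and tests not started because of intolerance, as not acceptable. Set physical impossibility aside as not applicable. Keep any rating actually given by a patient who stopped early.

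Beside both, show the counts refused, not tolerated, not possible and stopped early. State how the Likert scale is divided if a percentage acceptable is reported.

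No new data collection appears necessary, since Protocol 5.6 and 5.7 already provide for recording refusal, inability, discontinuation and the reasons exercise ABPI was not done or was ended early. The cost is that recorded reasons must be grouped before analysis, with some judgement where the clinical team made the decision, and the figures in (b) may be slightly less favourable.
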